At point-of-entry, data values will undergo consistency edits (e.g., ID validation, range verification, duplicate detection) and personnel will be required to correct errors. Data management staff will run logic error programs to check for accuracy and irregularities within and across data structures and within and across sites. Quality assurance checks will be conducted regularly by site personnel as well as by data management staff. Regularly scheduled, and as needed, communications between the study team, the neuroimaging team and PI will clarify any inconsistencies and ambiguities in the data.

Data Analysis

Power Analysis: **Aim 1A:** Based on differences in PPF in FXS vs. TDC in our resting state EEG data, we expect an effect size of approximately .8 to 1.1, similar to effect sizes in low gamma power and N1 amplitudes in FXS^{10, 12, 90, 91}. **Aim 2:** The effect size for WLI differences between structured and random conditions is approximately .8⁵³. The primary comparisons for both **Aim 1A** and **Aim 2** will be between diagnostic groups, FXS vs. TDC and FXS vs ASD. Therefore, to be statistically conservative, the nominal alpha of .05 will be divided by 4, i.e. .0125 per hypothesis. Using the available FXS vs. TDC effect size of 0.8, 40 subjects in each of the three diagnostic groups yields 84.3% power at a level of significance = .0125. Effects size data for FXS vs. ASD for these measures is not available but may be estimable for future studies. **Aim 3:** This aim is novel, without a strong basis for estimating an effect size. AAE effect size of PPF enhancement (vs. sham) in our preliminary data is between .89 and .97 (obtained peak frequencies of 9.3 to 9.6 Hz). For the within-groups crossover, an AAE trial to detect treatment differences in a 2 X 2 crossover design (20/group) yields approximately 80% power to identify group differences with an effect size of .9 at an alpha of 0.05.

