Statistical analysis: PPF (**Aim 1A**) and WLI (**Aim 2**) were selected as primary response variables since they will be individually optimized as starting parameters in **Aim 3**. Planned comparisons include FXS vs. TDC and FXS vs. ASD. FXS vs. TDC will be of primary interest, but confirmation of FXS vs. ASD can weaken the inference that differences in intellectual ability and genetic liability alone account for group difference. **Covariates:** FXS vs. TDC model will include age, sex, and non-verbal IQ. FXS vs. ASD will additionally include co-occurring psychiatric diagnoses, psychiatric medication(s) (4 categories), and SRS score. A group by sex interaction will be added to each model given known sex

differences in FXS¹⁵. **Aim 1B:** Murine data will consist of a parallel model to Aim 1A with three neurodynamic variables (PPF, event duration, and event number) and independent variable of group (KO or WT; 80 in each group). **Aim 3:** A linear model with repeated measures will test a 2-treatment, 2-period, 2-sequence balanced-crossover design (Williams, 1989) with Kenward-Roger adjustment⁹² applied. Further, as in Aim 1A and 2, two separate models will be examined for FXS vs. TDC and FXS vs. ASD. The responses of interest in Aim 3 are 40Hz ITC and WLI change (AAE vs. sham). The fixed effects of diagnostic group, treatment, the interaction between diagnostic group and treatment, treatment sequence, and period will be examined. Potential carryover effects will also be assessed. **Covariates:** Covariates for each comparison will be identical to models for Aim 1A and 2 above. The adjusted (least squares) means for the diagnostic group by treatment combination will allow to compare within and between diagnostic groups. Within the FXS group, for example, the treatment effect will be by testing the contrast (FXS treatment – FXS sham) at the 0.05 level of significance.

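### Aim 3 has two primary endpoints and two group models, but it is powered and tested at .05 per test with no multiplicity rule, although the plan divides alpha by 4 for the parallel structure in Aims 1A and 2

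*Combined protocol and SAP*

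**What the plan says.** All of the relevant text is in section 14.0 (Data Analysis), except the endpoint list in section 4.0.

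- **Aims 1A and 2.** The primary comparisons "will be between diagnostic groups, FXS vs. TDC and FXS vs ASD". The plan then says that "to be statistically conservative, the nominal alpha of .05 will be divided by 4, i.e. .0125 per hypothesis". Power is computed at that level: "Using the available FXS vs. TDC effect size of 0.8, 40 subjects in each of the three diagnostic groups yields 84.3% power". The Statistical analysis paragraph names PPF (Aim 1A) and WLI (Aim 2) as the primary response variables.
- **Aim 3, endpoints.** Section 4.0 lists two primary endpoints: the AAE-versus-sham change in 40 Hz ITC, and WLI in the passive task. Only the reaction-time outcome is labelled exploratory.
- **Aim 3, models.** The analysis text says that "as in Aim 1A and 2, two separate models will be examined for FXS vs. TDC and FXS vs. ASD".
- **Aim 3, significance level.** The design "yields approximately 80% power to identify group differences with an effect size of .9 at an alpha of 0.05". For the FXS group, given as an example, "the treatment effect will be by testing the contrast (FXS treatment – FXS sham) at the 0.05 level of significance".

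The only ordering stated anywhere is that "FXS vs. TDC will be of primary interest". No adjustment, testing sequence or both-endpoints rule is given for Aim 3.

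**The concern.** Aims 1A and 2 together have two primary variables and two group comparisons, and the plan pays for them by dividing alpha. Aim 3 also has two primary endpoints and two group comparisons, but .05 is the only level given. The plan does not explain the difference.

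Aim 3 is the randomised, sham-controlled part of the project. As written, an AAE effect could be claimed from either endpoint, from either model, and from either the within-FXS contrast or the group-by-treatment interaction. Nothing says in advance which of these counts. The false-positive rate for the aim is then above 5%, and the deciding contrast could be chosen after the results are seen. If the error rate is controlled, the stated power no longer applies per test at the plan's own effect size.

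**Working it through.** **1. Reproduce the plan's figure for Aims 1A and 2.** Inputs: effect .8, 40 vs 40, alpha .0125. Two-sided two-sample noncentral t: ncp = .8 × √(40/2) = 3.578, df 78. Power is 84.3%, an exact match. Section 14.0 does not say what the 4 counts. Two primary variables × two comparisons = 4 is the natural reading.

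**2. Reproduce the Aim 3 figure.** Inputs: effect .9, 20 per group, alpha .05. The plan does not state sidedness; two-sided is assumed because it reproduces the plan's figures. By the same method, ncp = .9 × √(20/2) = 2.846, df 38. Power is 79.2%, which agrees with the stated figure. The normal approximation gives Φ(2.846 − 1.960) = 81.2%.

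**3. Same calculation at smaller alphas (power per test).**

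| Alpha | Noncentral t, df 38 | Normal approximation |
|---|---|---|
| .05 | 79.2% | 81.2% |
| .025 (two endpoints) | 69.5% | 72.7% |
| .0125 (four tests) | 59.1% | 63.6% |

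**4. Sensitivity to the undefined SD.**

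- If .9 is in SDs of the within-subject AAE-minus-sham difference, ncp = .9 × √20 = 4.025. Power with df 18–19 is about 97% at .05, 93% at .025 and 88% at .0125. This reading does not reproduce the stated 80%.
- If .9 is in within-subject SDs, the SD of the difference is √2 times larger and ncp is again 2.846. With variance pooled over two groups (df 36), power is 79.1%, 69.3% and 58.9%. With FXS alone (df 18), it is 76.8%, 65.7% and 54.1%.

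**5. Familywise error with no AAE effect, .05 per test.** Two independent tests give 1 − .95² = 9.75%, and four give 1 − .95⁴ = 18.5%. The Aim 3 tests are not independent, because both models use the same 20 FXS participants and the endpoints may be correlated. A simulation was therefore run with 20 per group, equal SDs, two-group models with group and period terms, and endpoint correlation 0, .3 and .5. The correlations are assumed.

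| Tests used | Chance of at least one p<.05 (correlation 0 / .3 / .5) |
|---|---|
| FXS AAE-sham contrast, one model, two endpoints | 9.7% / 9.5% / 9.1% |
| The same contrast, both models | 11.7% / 11.4% / 10.9% |
| Four group-by-treatment interactions | 17.2% / 16.8% / 16.2% |

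For the four interactions I quote 16–18%, to leave a small margin for modelling detail. At .0125 per test they give 4.6–4.7%.

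**6. Effect detectable with 80% power at 20 per group.** Solve for δ with ncp = δ√20, where δ is in SDs of the AAE-sham difference within FXS. At .025, δ is 0.71 if variance is pooled over the two groups in the model (df 36–37) and 0.74 from FXS alone (df 18–19). For the FXS-vs-control difference in response at .0125 (ncp = δ√10), it is 1.10.

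**7. Holm over the two endpoints, FXS contrast, both responding at .9 in within-subject SDs (.9/√2 = .636 SD of the AAE-sham difference).** First-step power per endpoint is about 69%. Overall power per endpoint is 75–77%, and power for at least one endpoint is 84–91% (correlation 0 to .5).

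**The case against.** **Separate families are defensible.** The plan does not say that the division by 4 extends to Aim 3, and a sponsor may treat the trial as its own family. That stands. A reader might infer that the plan breaks its own rule, or that Aim 3 must be tested at .0125. The documents do not support that. But within an Aim 3 family there are still two primary endpoints and two models, each at .05.

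**The parallel is not exact.** Section 4.0 lists more outcomes of primary interest for Aim 1 than the single PPF variable in section 14.0. Aim 2 tests a group difference in WLI, while Aim 3 tests an AAE-versus-sham change. Different levels for different hypotheses are not in themselves a contradiction.

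**Four is too many for the contrast that is written out.** The FXS AAE-sham contrast in the second model largely repeats the first. Using both models raises the error only from 9–10% to 11–12%. Two endpoints call for .025, not .0125. This stands, and .0125 fits only if the four interactions are primary.

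**Power may hold up better than the per-test figures suggest.** A reader might conclude that power falls to 54%, or that 20 per group is too few. The 54% comes only from the df 18 variant, which gives 76.8% at .05 and so fits the stated figure less well. On the paired-difference SD, power would be about 88% even at .0125, although that reading does not match the plan's 80%. With Holm, the chance of success on at least one endpoint is above 80% if both respond at .9.

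**There is an informal ordering, and the aim is novel.** Calling FXS vs. TDC the main interest is not a testing sequence, and it leaves two endpoints. The plan's remark that Aim 3 lacks a strong basis for an effect size concerns sizing, not error control.

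**Conclusion.** The point holds as a missing decision rule. Aim 3 has two primary endpoints and two group models, is powered and tested at .05, and has no hierarchy or adjustment. Followed as written with no AAE effect, it gives at least one p<.05 in about 9–10% of trials for the FXS contrast on two endpoints in one model, 11–12% across both models, and 16–18% for the four interactions. These rates assume equal SDs and endpoint correlation between 0 and .5.

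Power per test at the plan's effect of .9 is about 69% at .025 and 59% at .0125 (73% and 64% by normal approximation), against 79% (81%) at .05. These figures depend on the reading of .9 that reproduces the plan's 80%. They do not show that the trial is too small. The plan should be corrected, and a change of text is enough.

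**What to change.** **In the Statistical analysis paragraph of section 14.0, name the decisive Aim 3 test.** One workable wording, which follows the plan's stated interest in FXS vs. TDC:

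> The primary Aim 3 test is the FXS AAE-minus-sham contrast from the FXS vs. TDC model, for 40 Hz ITC and WLI, with Holm adjustment at familywise .05. All other contrasts, including those from the FXS vs. ASD model, are secondary.

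Alternatives:

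- Name one endpoint and one contrast as the single primary test and keep .05. This costs no power but demotes one primary endpoint.
- If the four FXS-vs-control interactions are meant to be primary, use .0125 each. Power at .9 is then about 59% per test, and the effect detectable with 80% power is 1.10 SD of the AAE-sham difference.

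**In the Power Analysis paragraph, restate power at the chosen alpha and say which SD the effect size uses.** For the Holm option:

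> At .025 with 20 per group there is 80% power for about 0.71 SD of the AAE-sham difference if variance is pooled across the two groups in the model (0.74 SD from FXS alone).

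Add that the .89–.97 range is a PPF effect, and that the plan gives no AAE effect size for 40 Hz ITC or WLI.

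**Cost.** Under Holm, first-step power per endpoint at .9 falls from about 79% to about 69%. If both endpoints respond at .9, it is 75–77% per endpoint overall and 84–91% for at least one. No added enrolment is needed. The choice among these options is the sponsor's and should be fixed before unblinding.

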2.0 Objectives

Our **central hypothesis** is that in Fragile X Syndrome (FXS), reduced alpha (~10 Hz) pacing and increased gamma (>30 Hz) noise impairs, via altered timing, the detection of sensory patterns and the ability to mount precise neural responses, thereby impeding cognitive functioning and contributing to increased sensory hypersensitivity. Our **approach** involves three scientific aims, which, if addressed, would ascertain underlying mechanisms that may alleviate sensory and cognitive impairments.

Specific Aim 1: Translational neurodynamics in resting and sensory studies. We hypothesize that fine-temporal alpha and gamma neurodynamics will uncover the basis of participant- and subgroup-level variation that drives FXS group effects. **1A:** We will acquire resting-state electroencephalography (EEG) and sensory auditory chirp paradigms in 40 youth (5 to 15 years old) with FXS and age- and sex-matched typically developing controls (TDC) and autism spectrum disorder controls (ASD). Neurodynamics (peak power frequency, spectral events) and biophysical modeling of each paradigm will be compared between groups. Neurodynamics will be assessed individually and in combination as predictors of psychological measures, medication effects, co-occurring neuropsychiatric diagnoses, and computerized cognitive testing. **1B:** We aim to identify neurodynamic features that distinguish *Fmr1^{-/-}* KO from wild type (using preexisting resting-state EEG and sensory auditory chirp murine data). **1C (Exploratory):** We aim to identify neurodynamic features that are conserved between *Fmr1^{-/-}* KOs and participant human subgroups based on genotype. We hypothesize that full mutation, non-mosaic males with FXS will share similar neurodynamics as the *Fmr1^{-/-}* KO (knockout) mouse. Shared neurodynamics between *Fmr1^{-/-}* KO and a human subgroup will have a high translational impact.

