9.0 Local Number of Subjects

The target enrollment for the case-control portion (Aims 1 & 2) is 120 subjects and 60 subjects for the clinical trial (Aim 3), for a total of 180 subjects across all aims. We plan to recruit a total of 60 subjects with Fragile X Syndrome with full FMR1 mutations (>200 CGG repeats; at least partial FMR1 gene methylation). Of these FXS subjects, 40 will be recruited for the case-control portion and 20 will be recruited into the clinical trial. The overall project will recruit an additional two cohorts of control subjects for a total of 60 IQ-, sex-, and chronologically aged matched non-syndromic (i.e., idiopathic) ASD controls, and 60 sex-and chronologically aged matched TDCs. Following completion of the case-control portion, subjects and their guardians may be asked to participate in the clinical trial portion of the study.

Retention Plan: We do not anticipate a high drop-out rate since almost all testing is non-invasive, and each portion of the study (case-control and clinical trial, respectively) can be completed in 2 visits, with ample time allowed between visits. Thus, we expect close to 90% retention of all recruited subjects. Subjects unable to complete study procedures or who fail to consent/withdrawal following enrollment will be replaced to maintain our enrollment target of 180 total subjects.

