Exploratory analyses: **Aim 1A:** Other neurodynamic response variables (event rate and event duration) and chirp response (40Hz ITC and gamma ERSP) will be modeled as PPF. If the sex x diagnostic group interaction is significant ($p < .05$), subsequent post-hoc inter-diagnostic comparisons will be made for each sex. Lastly, for Aim 1A, the five variables representing neurodynamics and chirp response (PPF, event rate, event duration, 40 Hz ITC, and gamma ERSP) will be examined as a multivariate response across two paradigms (rest and chirp). As in the models above, diagnostic group will be the independent variable along with the appropriate covariates as described above. **Aim 1C:** To identify which FXS genotype (males with or without mosaicism and females) has similar alterations in neurodynamic variables as the Fmr1-/- KO (vs. WT) we will derive 95% confidence intervals for the effect sizes for each of the three neurodynamic variables for each of the three FXS subgroups (vs. their respective matched controls) and compare to the confidence interval for the effect size based on the Fmr1-/- KO vs. WT comparison. Lastly, significant differences between the FXS effect sizes and the murine effect size will be explored using bootstrap methodology where the resampling will be within each subgroup (human and mouse).

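### Aim 1C seeks the FXS subgroup that resembles the knockout mouse, but neither of its planned comparisons can show similarity

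*Combined protocol and SAP*

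**What the plan says.** The combined protocol and SAP, Section 14.0 (Data Analysis, Exploratory analyses), gives the purpose of Aim 1C: "To identify which FXS genotype (males with or without mosaicism and females) has similar alterations" to those of the knockout mouse. There are two steps. First, the analysts will "derive 95% confidence intervals for the effect sizes for each of the three neurodynamic variables for each of the three FXS subgroups", each against its own matched controls, and "compare to the confidence interval for the effect size based on the Fmr1-/- KO vs. WT comparison". Second, "significant differences between the FXS effect sizes and the murine effect size will be explored using bootstrap methodology", with resampling inside each human and mouse subgroup.

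Section 2.0 (Specific Aim 1) labels Aim 1C exploratory and names the expected match: non-mosaic males with full mutation "will share similar neurodynamics as the" knockout mouse. It attaches high translational value to such a match.

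On numbers, Section 9.0 states "Of these FXS subjects, 40 will be recruited for the case-control portion". The statistical analysis paragraph of Section 14.0 gives 80 knockout and 80 wild-type mice. The documents state no subgroup sizes, no murine effect size, no similarity criterion and no margin for Aim 1C.

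**The concern.** The question is about similarity, but both tools are built to detect difference. Wide intervals overlap easily, and a test with few children seldom reaches significance. If either result is reported as resemblance, imprecision is read as biological agreement. Forty children divided among three genotypes will give wide intervals, so a subgroup with no alteration at all could be described as mouse-like. If the subgroups also differ in size, a smaller non-matching subgroup would look mouse-like more often than a larger one.

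What is at stake is the credibility of a human-mouse match that the protocol itself presents as important. No treatment comparison depends on it.

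**Working it through.** **The plan's nearest stated figure.** Aim 1C has no power statement. The power paragraph of Section 14.0, for Aims 1A and 2, reads "Using the available FXS vs. TDC effect size of 0.8" with 40 per group and a significance level of .0125, giving 84.3%. A two-sided two-sample t-test with noncentrality 0.8 × √(40/2) = 3.578 on 78 degrees of freedom gives 84.33%. The figure reproduces.

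**Inputs for Aim 1C.**
- From the documents: 80 mice per group and 40 FXS children in three subgroups, which is about 13 each if even. The Study Summary lists 60 FXS for the case-control part; that would be 20 each, which lies inside the range used here.
- Assumed: murine d of 0.8 or 1.0 (the plan's human range for FXS vs. TDC is about 0.8 to 1.1); 8, 13 or 20 children per subgroup, with equal numbers of controls; a human subgroup with no alteration (d = 0).

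**Formulas.** With n per group, SE(d)² = 2/n + d²/(4n), and the 95% half-width is 1.96 × SE.
- Intervals overlap when |d_human − d_mouse| ≤ 1.96 × (SE_human + SE_mouse).
- The difference is non-significant when |d_human − d_mouse| ≤ 1.96 × √(SE_human² + SE_mouse²).

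**Worked case (murine d = 0.8, n = 13).**
- Mouse: SE² = 0.025 + 0.002 = 0.027, SE = 0.164, half-width 0.322.
- Human at d = 0: SE² = 2/13 = 0.154, SE = 0.392, half-width 0.769.
- SD of the difference: √(0.154 + 0.027) = 0.425.
- Overlap limit 0.769 + 0.322 = 1.091. Probability Φ((1.091 − 0.8)/0.425) = 75.3%; the other tail is negligible.
- Non-significance limit 1.96 × 0.425 = 0.834. Probability Φ((0.834 − 0.8)/0.425) = 53.1%.

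**Chance that a subgroup with d = 0 gives each result, on one variable:**

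| n per subgroup | Overlap, murine 0.8 | Non-significant, murine 0.8 | Overlap, murine 1.0 | Non-significant, murine 1.0 |
|---|---|---|---|---|
| 8 | 83.0% | 67.0% | 72.1% | 52.5% |
| 13 | 75.3% | 53.1% | 59.0% | 35.0% |
| 20 | 65.5% | 38.8% | 44.3% | 20.2% |
| 40 | 44.3% | 17.8% | 20.2% | 5.3% |

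At murine d = 1.1 and n = 13, overlap is still 50%. A true match overlaps about 99% of the time at every size, so overlap separates a match from no alteration poorly at these sizes. If all three variables had to overlap and were independent (an assumption), the 75.3% becomes 0.753³ = 43%.

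**Unequal subgroups.** In a simulation with an assumed 20/8/12 split, murine d = 0.8 and no alteration in any subgroup, overlap occurred 66%, 84% and 77% of the time, and a non-significant difference 39%, 68% and 55%. The subgroup of 8 looked mouse-like most often.

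**Ranking by the closest estimate instead.** With the same split and true d of 0.8, 0 and 0, the correct subgroup was chosen about 74% of the time. With all three at 0, each was chosen 31% to 35% of the time, so size mattered little.

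**Would an equivalence margin of ±0.5 SD work?** With all 40 FXS children in one subgroup, the narrowest possible 95% interval for the difference has half-width 1.96 × √(2/40 + 2/80) = 0.537. That exceeds 0.5, so the criterion could never be met. With a 90% interval and a true d of 0.8 in both species, power is about 9% at 40 per group and zero at 13.

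**The case against.** The strongest reply is that the plan says only that the intervals will be compared. A reader might infer that it adopts overlap, or non-significance, as its definition of similar. The text does not say so. What is established is that no criterion is given and that the two tools cannot supply one.

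A reader might also infer that the method inherently favours the smallest subgroup. That does not follow. Subgroup sizes are not stated, equal sizes remove the tilt, and another natural reading reverses it. Suppose a subgroup must also show an alteration of its own, with a CI that excludes zero in the murine direction. A subgroup with d = 0 then passes only about 2% of the time at any size. A true match at murine d = 1.0 passes about 47%, 68%, 86% and 99% of the time at 8, 13, 20 and 40 per group, so small subgroups are then disadvantaged. This reading is not written in the plan either, but it shows how far the answer depends on the missing criterion.

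Two further replies stand. The bootstrap compares the two species directly and has lower false-similarity rates than overlap. And the planned outputs do give an effect size with a CI for every subgroup and variable, so it would be wrong to say that they cannot indicate which subgroup is closest. Neither reply turns a non-significant difference into evidence of similarity.

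Exploratory status is a fair reason to rate the point low. It excuses low power, but not reading imprecision as resemblance.

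**Conclusion.** The point holds in a limited form. Aim 1C poses a similarity question and plans only a comparison of separate CIs and a search for significant differences; neither overlap nor non-significance answers it. For a subgroup with no alteration, the chance of appearing mouse-like on one variable is about 44% to 83% by overlap and 20% to 67% by non-significance. These ranges rest on an assumed murine d of 0.8 to 1.0, on 8 to 20 children per subgroup with as many controls, and on overlap or non-significance being read as similarity. An advantage for a smaller non-matching subgroup arises only under that reading and only with unequal sizes.

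This is a cheap improvement of minor weight. Aim 1C is exploratory and feeds no primary endpoint, sample size calculation or Aim 3 treatment comparison.

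**What to change.** Reword the Aim 1C paragraph in Section 14.0, before human and mouse results are compared, so that:

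- the planned bootstrap of the human-mouse difference is the main Aim 1C analysis;
- for each subgroup and variable, the human-minus-mouse difference in effect size is reported with its CI, beside the subgroup's own effect-size CI, so that the reader can see whether there is an alteration in the murine direction;
- subgroups are ranked by estimated distance from the mouse, with bootstrap uncertainty for the ranking;
- overlap of intervals, or a non-significant difference, will not be reported as similarity;
- subgroup sizes are shown with every result.

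An equivalence margin of ±0.5 SD should not be the decision rule, because it is unattainable with this sample.

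The cost is wording and modest programming; the resampling is already planned and no new subjects, visits or data are needed. The downside is that small subgroups will mostly be reported as inconclusive, which is what these data can support.
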